4 EXPERIMENTAL PLAN

4.1 Study Design

This is a multi-center, OLE study for patients with DS or LGS who have completed the double-blind, placebo-controlled, clinical studies of GWP42003-P (Core Studies). The study consists of a titration period and a maintenance period, followed by a 10-day taper period.

Titration Period: All patients will titrate up to 10–20 mg/kg/day GWP42003-P using a recommended titration schedule (see [APPENDIX 4](#)). It is advised that the Investigator considers monitoring hepatic function (alanine aminotransferase [ALT], aspartate aminotransferase [AST], total bilirubin [TBL] and international normalized ratio [INR] levels) during the titration period for patients taking concomitant AEDs that are known to be associated with hepatic injury or failure. To minimize any elevations in hepatic function markers the titration period can be extended and the dosage of a concomitant AED and/or GWP42003-P may be adjusted at the discretion of the Investigator. If there is intolerance during titration, the patient may be maintained on a dose below 10–20 mg/kg/day. A titration rate faster than recommended may be considered if there is an increase in seizures, following consultation with the GW medical monitor.

Maintenance Period: Patients will continue dosing at 10–20 mg/kg/day. However, Investigators may decrease the dose if the patient experiences intolerance, or increase the dose if required for better seizure control, until the optimal dose is found. The Investigator may schedule additional clinic visits to facilitate dose adjustments e.g., when increasing doses above 20 mg/kg/day. Patients whose dose has been decreased can have their dose increased again provided there is adequate tolerance. The maximum dose patients can receive will be 30 mg/kg/day (51 mg/kg/day is the maximum dose safely used in the USA EAP to date with a mean dose of 24 mg/kg/day [$n = 59$]). Dose increases above 20 mg/kg/day are recommended to be done slowly, with maximum increments of 2.5 mg/kg every 5–7 days. If seizure freedom is achieved with use of GWP42003-P during the study, the Investigator can consider reducing the dose of concomitant AEDs after consultation with the GW medical monitor.

Study Completion: The maximum duration of this OLE study will be 4 years (208 weeks after Visit 1).

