- A patient with at least 2 years' participation in the OLE (≥ 104 weeks after Visit 1) will complete the OLE phase when GWP42003-P is approved in their indication and is commercially available. Patients will complete an

unscheduled 'End of treatment' visit to transition from OLE to commercial product. The timing will vary per patient and is projected to begin in February 2019.

- A patient with less than 2 years' participation in the OLE when GWP42003-P is approved in their indication and is commercially available will continue the OLE phase until reaching a maximum of 2 years' (104 weeks after Visit 1) OLE treatment, at which point an unscheduled 'End of Treatment' visit will be conducted. The unscheduled 'End of Treatment' visit will be conducted no earlier than 730 days after Visit 1.
- A patient who does not continue treatment with GWP42003-P will commence the 10-day taper period (down-titrating 10% per day for 10 days) and complete an 'End of Taper Period' visit followed by a Follow-up visit (which can be by telephone) 4 weeks later.

Interim Analysis: At least one interim analysis will be conducted to support New Drug Application and Marketing Authorization Application filings. Further interim analyses may be conducted as required.

A study schema ([Figure 1-1](#)), presented at the end of [Section 1](#), depicts the overall study design. More detailed information on treatment and study procedures is provided in [Section 8](#) and [Section 9](#), respectively, and is summarized in [APPENDIX 1](#).

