4. STATISTICAL METHODS

4.1 General Considerations

All tables will be presented by indication (where appropriate), including an overall count, as follows:

Dravet Syndrome (N=XX)	Lennox-Gastaut Syndrome (N=XX)	Overall (N=XX)
------------------------	--------------------------------	----------------

In all tables, listings and figures, the study visits will be referred to and labelled as per [Table 2](#)

Table 2 Study Visits

Actual Visit	Visit Label
Visit 1: Day 1	Day 1
Visit 2: Day 15	Day 15
Visit 3: Day 29	Day 29
Visit 4: Day 85	Day 85
Visit 5: Month 6 or Week 24	Week 24
Visit 6: Month 9 or Week 38	Week 38
Visit 7: Week 48 or End of Treatment (only patients who completed at 1 year)*	Week 48
Visit 8: Week 76	Week 76
End of Treatment (only patients who completed on or after Day 400)*	End of Treatment

End of Treatment (withdrawn patients only)	End of Treatment
End of Taper	End of Taper
Post-Taper Safety Call	Post-Taper Safety Call
Safety Follow-Up	Safety Follow-Up

* For some patients, the end of treatment visit occurs after one year in the OLE, whereas for other patients the end of treatment visit occurs after two or more years in the OLE.

Unless stated otherwise, continuous variables will be summarized showing the number of non-missing values (n), mean, standard deviation, median, minimum and maximum and categorical variables will be summarized showing the number and percentage of patients falling in each category. For continuous summaries of seizure frequency, the lower and upper quartiles will also be presented.

Minimum and maximum values will be presented to the same decimal precision as the raw data. Mean and median will be presented to one more decimal place than the raw data, and standard deviation to 2 more decimal places than the raw data. Percentages will be presented to one decimal place.

For patients who enter the OLE on the same day as the core study end of treatment or end of taper visit, the CRF for this study did not require some data to be entered for a second time. Hence, for visit based endpoints, if a patient does not have data entered in this study at Visit 1, then data from the end of treatment or end of taper visit in the core study will be used, provided that the date of collection is on Day 1 of the OLE.

Unless otherwise stated, all summaries will be presented by indication.

All analyses and summaries will be produced using SAS Version 9.4.

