4.1.4.3 Last 12 Weeks

The last 12 weeks (84 days) for IVRS based endpoints is defined as all available data from 12 weeks prior to the earliest of the date of the patient completing/withdrawing from the study, the last call to IVRS, or the last dose date as recorded on the "End of Treatment Study Outcome" page of the CRF.

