- If the call takes place >7 days after the previous call, then the number of days since the last call will be 7.

For the seizure types and periods listed above, summary statistics will be presented for raw seizure frequencies and percentage change from baseline from core study baseline period. In addition, the number of patients with $\geq 25\%$, $\geq 50\%$, $\geq 75\%$ and 100% reduction in seizure frequency will be presented.

Furthermore, the percentage change from the core study baseline period will be presented for convulsive seizures from Dravet patients only and for drop seizures for LGS patients only.

All outputs will be repeated with the inclusion of an LOCF imputation step, which is described in the following steps:

- If a patient has valid data for ≥ 1 consecutive periods from and inclusive of the first period but only missing periods thereafter, then imputation of the missing period(s) will be carried out using the last 12 weeks of valid data (see Section 4.1.4.3).
- If a patient has intermittent missing periods (i.e. ≥ 1 missing period that falls after a populated period 1 and before subsequent populated periods), then the missing period(s) will be imputed with the closest earlier non-missing period of data.
- If the patient has ≥ 1 consecutive periods of missing data from and inclusive of the first period then no imputation will occur and data from the patient will be excluded from any LOCF presentations.

Summaries related to seizures as presented in this section and subsequent sections will include patients from all core studies except GWEP1332 Part A, from which data will be listed only.

The seizure frequency (per 28 days) and percentage change from baseline for total seizures, drop seizures and convulsive seizures during the study will be evaluated for the periods described in Section 4.5.9 and for the following subgroups:

- Patients taking clobazam
- Patients not taking clobazam
- Core study actual treatment: GWP42003-P
- Core study actual treatment: Placebo
- Patients taking clobazam; core study actual treatment: GWP42003-P
- Patients not taking clobazam; core study actual treatment: GWP42003-P
- Patients taking clobazam; core study actual treatment: Placebo
- Patients not taking clobazam; core study actual treatment: Placebo
- Patients with data at Week 37 (Day 253) to Week 48 (Day 336) [^]
- Patients with data at Week 37 (Day 253) to Week 48 (Day 336); patients taking clobazam [^]

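### In six seizure tables, the LOCF rule in SAP 4.5.9 imputes 12-week periods that planned completers were never due to have

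*SAP*

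**What the plan says.** - **Trigger (SAP 4.5.9).** The rule covers anyone who has seizure data from period 1 onwards and later has none at all. For them, "imputation of the missing period(s) will be carried out using the last 12 weeks of valid data". The rule sets no condition on the reason data stop and no last period.
- **Carried value (SAP 4.1.4.3, cited by the rule).** The last 12 weeks are "all available data from 12 weeks prior to the earliest of the date of the patient completing/withdrawing from the study", or the last IVRS call or last dose if earlier. Completers are therefore expressly covered.
- **Planned ends differ (SAP 4.1, Table 2 footnote).** "For some patients, the end of treatment visit occurs after one year in the OLE". The footnote puts the rest at two years or longer. SAP 3.1.3 makes the maximum treatment time depend on country.
- **Protocol 4.1.** "The maximum duration of this OLE study will be 4 years (208 weeks after Visit 1"). A patient with at least two years in the study "will complete the OLE phase when GWP42003-P is approved in their indication and is commercially available". A patient with less than two years at that point continues to two years, and the unscheduled final visit "will be conducted no earlier than 730 days after Visit 1".
- **Periods (SAP 4.5.9).** The list of 12-week periods is open-ended.
- **Outputs (SAP Table 12).** The LOCF tables are 9.1.1.2, 9.1.2.2 and 9.1.3.2 (total, drop and convulsive seizure frequency) and 9.7.2, 9.7.4 and 9.7.6 (the matching responder rates). Each has a twin without imputation.

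**The concern.** LOCF is meant for data that should exist and do not. A patient who finished the extension as planned at one year has no missing Week 193 to 204 record, because that period was never part of the patient's follow-up. The rule nevertheless treats it as missing and fills it with the exit value.

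Maintenance of seizure reduction is a secondary objective and endpoint. The SAP defines no separate analysis of it, so the by-period frequency and responder tables have to answer the question. In the LOCF versions, a carried patient is flat from exit onwards. Late columns then mix observed late response with copies of year-one or year-two response, and the SAP does not require the two to be counted separately.

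The rule also weakens the one thing LOCF could usefully do here, which is to check whether early withdrawal of poor responders flatters the late observed results. Pooling planned completers with withdrawals blurs that comparison.

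**Working it through.** **Inputs.** Period length is 84 days (SAP 4.5.9). Maximum duration is 208 weeks, or 1,456 days (Protocol 4.1). Planned ends are one year and two or more years (SAP Table 2), with Day 730 as the earliest unscheduled final visit (Protocol 4.1).

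**Check on the period limits.** Period k runs from Day 84(k − 1) + 1 to Day 84k. For k = 8 this gives Day 589 to 672, as in the SAP.

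**Full periods available.** 1,456 / 84 = 17.3, so 17 full periods.

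**Imputed share.** Observed periods = end day / 84, rounded up. This counts a part-filled last period as observed, because SAP 4.5.9 sets no minimum amount of data. Imputed = 17 − observed.

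| Planned end | End day | Observed | Imputed of 17 | Share |
|---|---|---|---|---|
| Week 48 | 336 | 4 | 13 | 76% |
| One year, up to Day 400 | 365 to 400 | 5 | 12 | 71% |
| Two years | 728 to 730 | 9 | 8 | 47% |

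The one-year range arises because Table 2 merges the Week 48 visit with the final visit of patients who completed at one year, and separates those completing from Day 400.

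**What this could do to a late column (assumed values only).** Let s be the share of patients carried forward, r the responder rate at planned end and q the true late rate. The last-period LOCF rate is s × r + (1 − s) × q. With r = 50% and q = 30%:

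- s = 50%: 25 + 15 = 40%
- s = 70%: 35 + 9 = 44%
- s = 80%: 40 + 6 = 46%
- s = 90%: 45 + 3 = 48%

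A true fall of 20 points would show as 10, 6, 4 or 2 points. The twin observed table would show 30% if planned end is unrelated to response.

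The effect also runs the other way. If response were 30% at exit and rose to 50% in those still treated, s = 70% gives 21 + 15 = 36%, and most of the improvement is masked. If response had already fallen to 30% before exit and stayed there, LOCF carries 30%.

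The documents give none of s, r or q.

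**The case against.** A reader might infer that the SAP shows long-term maintenance by construction and hides waning. The documents do not support that, for these reasons:

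- LOCF is a repeat of the outputs. All six imputed tables are labelled as LOCF and each has an observed-data twin. Waning among patients still in the study would appear in the twin. No table is titled as year-three or year-four data, and nothing assigns the maintenance endpoint to the LOCF versions.
- LOCF fixes the exit level, good or bad. Loss of response before exit is carried forward, and poor responders who withdraw early stay in the denominator.
- Not everyone is carried. Patients with the first period missing are excluded from LOCF, and GWEP1332 Part A is left out of all seizure summaries. An intermittent gap followed by trailing missing periods fits none of the three rules literally.
- Other displays help. There is a last-12-weeks summary, and a cohort with Week 37 to 48 data. Withdrawals are counted by 12-week period (SAP 4.4.2). The number of non-missing values is a standard statistic, so comparing twin frequency tables gives a rough imputed count.
- The study is descriptive, with safety as the primary endpoint.

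All of this stands, and it limits the point to the six tables. It does not remove it. The late observed columns rest on fewer and possibly selected patients, so a reader may turn to the fuller LOCF column, and the SAP does not say which version leads. A difference in n between twins does not separate planned completers from withdrawals, and SAP 4.4.2 does not count planned completions by period.

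**Conclusion.** The point holds for the six LOCF tables. The rule imputes periods beyond the planned end of treatment: 12 to 13 of 17 for a one-year completer and 8 of 17 for a two-year completer. These counts rest on 17 full periods in 208 weeks and on a part-filled period counting as observed. For these patients, change after exit cannot appear in those tables in either direction.

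The effect on reported frequencies and responder rates cannot be computed, because the documents do not give the numbers ending at one year, two years or later. For the same reason they do not establish that late LOCF columns consist mostly of carried values. The 40% to 48% figures only illustrate the mechanism. The observed tables are unaffected, so this is a fault in a companion analysis of secondary endpoints. It should be corrected before the tables are produced, but it does not undermine the study.

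**What to change.** Amend the LOCF steps in SAP 4.5.9 as follows:

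1. Do no trailing imputation for patients recorded as completing the treatment period, including those who move to commercial product.
2. For early withdrawals, carry forward only up to a defined cap: the maximum treatment duration that applied to that patient, by country (SAP 3.1.3) or by commercial availability (Protocol 4.1). The cap has to be written down, because an early withdrawal has no planned end date in the documents.
3. Print observed n and imputed n for each period in the six LOCF tables.
4. Name the observed tables as the main display for maintenance and the LOCF tables as supportive.
5. State how an intermittent gap followed by trailing missing periods is handled.

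The cost is a change of SAP wording and one derived end-of-treatment date per patient, plus smaller LOCF denominators in late periods. Completion status is already summarised under SAP 4.4.2. Whether the CRF separates a one-year planned end from a commercial transition is not shown in the documents, so the cap may have to be derived from country and approval dates.

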4.5.9.1 Status Epilepticus

The number of convulsive seizures greater than 30 minutes in duration and the number of non-convulsive seizures greater than 30 minutes in duration will be collected weekly via IVRS.

The number of patients with convulsive and non-convulsive seizures greater than 30 minutes in duration will be presented for each of the periods mentioned in Section 4.5.9.

4.6 Other Measures

4.6.1 Study Medication Use and Behavior Survey

This form consists of 18 questions regarding the use of the IMP. The trained investigator or study coordinator will complete this survey as an interview with the patient/caregiver at the final dosing visit (at the end of treatment or end of taper visit, as applicable).

The form will be completed for all patients 12 years of age and older in the study.

Each question will be summarized, on a categorical scale. Percentages will be based on the number of patients completing the survey.

4.6.2 Plasma Concentrations of CBD and its Major Metabolites

Plasma concentrations for CBD and major metabolites 7-carboxy cannabidiol and 7-hydroxy cannabidiol will be listed only for patients in the safety analysis set.

4.6.3 Plasma Concentrations of Concomitant AEDs

Blood sampling concentrations for AEDs will be listed only for patients in the safety analysis set.

4.6.4 Supplemental Drug Accountability Form

This form consists of 7 questions regarding various aspects of drug accountability and patient usage. It is completed as part of an interview with the patient/caregiver when a triggering drug accountability discrepancy is identified.

The triggering drug accountability discrepancies are as follows:

- Missing bottle(s).
- Compliance issues where one or more bottles are used compared to what was the expected use, according to the IVRS report and paper diary.
- Returned IMP supply with evidence of tampering.
- Greater than the target daily dose as recorded in the IVRS report and paper diary.

The number of patients completing a form will be summarized.

4.6.5 Supplemental Adverse Event Form

This form consists of 15 questions regarding the AE and use of IMP. It is completed as part of an interview with the patient/caregiver when a triggering AE of interest is reported.

The categories for triggering AEs of interest are:

- Euphoria or inappropriate elation.
- Inappropriate laughter or exhilaration.
- Mood changes.
- Drunk, high or intoxicated.
- Hallucinations (visual or auditory), dissociations, disorientation, agitation.
- Disturbance in cognition, memory, or attention.
- Drug abuse.
- Drug withdrawal or drug withdrawal syndrome.

- Addiction.
- Overdose.
- Misuse of IMP.
- Thoughts of suicide, attempted suicide or suicide.

The number of patients completing a form will be summarized.

4.6.6 Site Classification Form

The investigator reviews the applicable Supplemental Adverse Event Form or Supplemental Drug Accountability Form, and then completes a Site Classification Form. For each Supplemental Adverse Event Form or Supplemental Drug Accountability Form completed, there should be an associated Site Classification Form.

The Site Classification Form requires the investigator to assign the finding to an appropriate classification and then to also assign the possible relationship to the IMP. The investigator is also required to indicate the level of the certainty of the classification.

The number of patients completing a form and the possible relationship and level of the certainty for each category will be summarized, on a categorical scale. If more than one form is completed for a particular patient then they will be summarized under each category for all forms. However, if more than one form is completed with and assigned to the same category, then 'related' would be used over 'not related' and the highest level of certainty will be used for the corresponding chosen relationship.

4.7 Changes in the Conduct of the Study or Planned Analysis

A number of additional summaries have been added, compared to the protocol, and are described in the sections above. These additions are not detailed in this section.

The following endpoints described in the protocol are not included as part of the planned analysis in this SAP due to the nature of the collection of data for the endpoint not being compatible with a continuous summary of change from baseline:

- Change in the number of inpatient epilepsy-related hospitalizations (number of hospitalizations due to epilepsy in each 28-day period), relative to the pre randomization baseline of the Core Study.
- Change in the use of rescue medication (number of days used in each 28 day period), relative to the pre-randomization baseline of the Core Study.
- Change in the number of episodes of status epilepticus, relative to the pre randomization baseline of the Core Study.

The following endpoints described in the protocol are not included as part of the planned analysis in this SAP as they were not deemed necessary for the assessment of the objectives of this trial:

- Number of patients experiencing a > 25% worsening, – 25 to + 25% no change, 25–50% improvement, 50–75% improvement or > 75% improvement in total seizures, relative to the pre-randomization baseline of the Core Study.
- Percentage change in the frequencies of subtypes of seizures, relative to the pre-randomization baseline of the Core Study.
- Percentage change in total non-convulsive seizure frequency, relative to the pre-randomization baseline of the Core Study.
- Number of patients experiencing a > 25% worsening, – 25 to + 25% no change, 25–50% improvement, 50–75% improvement or > 75% improvement in convulsive seizures, relative to the pre-randomization baseline of the Core Study.
- Percentage change in the number of non-drop seizures, relative to the pre-randomization baseline of the Core Study.
- Number of patients experiencing a > 25% worsening, – 25 to + 25% no change, 25–50% improvement, 50–75% improvement or > 75% improvement in drop seizures, relative to the pre-randomization baseline of the Core Study.

In addition, the protocol included summaries of medical history. However, this was not collected as part of the OLE and is reported as part of the core studies only.

